2.0 OBJECTIVES AND SCIENTIFIC AIMS

- **Primary objective**: To determine if prophylactic use of a NPWT system on clean or clean-contaminated, closed incisions reduces incidence of post-operative wound complication which includes at least one of the following: wound separation as diagnosed by gross observation, wound seroma or hematoma as defined by the clinical or radiographic presence of fluid or blood collection in wound, and wound infection as defined by the presence of purulent discharge requiring exploration and/or cellulitis requiring the use of antibiotics, in patients with gynecologic malignancies undergoing laparotomy, and morbidly obese women undergoing laparotomy for any reason.
- **Secondary objective**: To determine the impact of NPWT on the incidence of specific type of wound complication as listed above.
- **Tertiary objective**: To report the incidence of adverse events such as blistering and contact dermatitis associated for each arm as per the published MSK Secondary Surgical Events system (Appendix D).

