4.2 Intervention

We propose the use of the Prevena Incision Management System, a subtype of the the V.A.C.® negative pressure wound therapy system (KCI, San Antonio, TX), for patients randomized to the intervention arm of our study.

The Prevena Therapy System will be applied at the time of wound closure in a sterile field for all patients who have undergone laparotomy, meet study inclusion criteria, and are randomized after the time of skin closure to the intervention arm of the study.

- The Prevena system will be left on for a minimum of 2 days and up to a maximum of 7 days as per product manufacturer recommendation.
- The Prevena system will be removed on the day of day of discharge or post-operative day 7, whichever occurs first.
- Patients who randomize to the standard dry gauze arm will have their dressing removed on post-operative day 2 (or before if clinically indicated)
- Evaluation for wound complications will be performed through provider-completed data collection sheets on the day of discharge (or POD 7), at the time of the Prevena system removal. Another evaluation will be performed during the patient's routine post-operative visit, which will occur at 30 days +/- 5 days after the day of surgery. Ongoing evaluation and documentation via phone calls, ugent care visits and nursing

follow-up, as per institutional guidelines, are in place to collect information throughout this time period.

- Patients who are unable to return for their post-operative visit before POD 35 will be contacted via telephone by a study investigator to complete a wound assessment based on what the patient reports.
- Patient follow-up will cease at the time an "event" is documented even if prior to the planned 30-day follow-up period. An event refers to one of the following:
 - Wound infection
 - Wound separation
 - Wound seroma
 - o Wound hematoma

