9.0 TREATMENT/INTERVENTION PLAN

- Patients who are randomized to the intervention arm of our study will undergo planned laparotomy with routine primary closure of their surgical incision at the completion of the case. Staples will be used for skin closure after standard fascial closure with PDS suture.
- Immediately thereafter, the experimental Prevena Therapy System will be applied to the closed, clean or clean-contaminated surgical incision.
- The Prevena[™] Customizable[™] dressing will then be connected to the Prevena 125 Therapy Unit to maintain a constant negative pressure of -125 mmHg.
- The Prevena system will be left on for a minimum of 2 days and up to a maximum of 7 days while the patient remains in the hospital post-operatively.
- All Prevena systems will be removed on the day of discharge or post-operative day 7, whichever occurs first.
- Evaluation for wound complications will be performed through provider-completed data collection sheets. These evaluations will be performed on the day of discharge (or POD 7 at the time of Prevena system removal) and at the patient's routine post-operative visit, which will occur at 30 days +/- 5 days after the day of surgery.
- Ongoing evaluation and documentation via phone calls, urgent care visits and nursing follow-up are in place to collect information throughout this time period as per institutional guidelines.
- Patients who are unable to return for their post-operative visit before POD 35 will be contacted via telephone by a study investigator to complete a wound assessment based on what the patient reports.
- Patient follow-up will cease at the time an "event" is documented even if it occurs prior to the planned 30-day follow-up period. An event refers to one of the following:
 - Wound infection
 - Wound separation
 - \circ Wound seroma
 - \circ Wound hematoma

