12.0 CRITERIA FOR THERAPEUTIC RESPONSE/OUTCOME ASSESSMENT

The primary outcome is the observed reduction of wound complications which includes at least one of the following:

- Wound separation as diagnosed by gross observation
- Wound seroma or hematoma as defined by the clinical or radiographic presence of fluid or blood collection in wound
- Wound infection as defined by the presence of purulent discharge requiring exploration and/or cellulitis requiring the use of antibiotics.

Secondary outcomes of wound blistering and contact dermatitis as related to adverse effects of either dressing.

Grading for complications will be captured as per the published MSK Secondary Surgical Events system (Appendix D) and documented for all cases of wound complication.

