13.0 CRITERIAFOR REMOVAL FROM STUDY

Patients will be removed from the study for any of the following reasons but they will not be replaced (see ntention to treat analysis below):

- If at any time the patient is found to be inevaluable for the protocol as designated in the section on Criteria for Patient/Subject Eligibility (e.g., a change in diagnosis), she will be removed from the study.
- If the patient decides to withdraw consent or discontinue participation in the study, she will be removed from the study; however, the Prevena will only be removed for medical reasons and not because the patient is withdrawing from the study.

The following patients will come off study, but they will be included in the analysis:

- If the Prevena Incision Management System is removed prior to 2 days after initial placement, the patient will be included in the analysis as a failure.
- If the patient experiences any grade 4 toxicity as per the MSK Secondary Surgical Events system.

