The primary objective analysis of our study will be performed via a two sample test for binomial proportions to compare the difference in proportions between the 2 arms at a type I error of 10%. We will also estimate the proportion of patients with post-op wound complication within 30 days and 90% Confidence interval for each arm assuming binomial proportions. We will perform an intent to treat (ITT) analysis where all patients who were randomized will be included in the analysis in the arm they were randomized to. If the Prevena Incision Management System is removed prior to 2 days after initial placement, the patient will be included in the analysis as per ITT and they will be considered as failures. We expect that <5% of the enrolled patients will have the Prevena system removed prior to 2 days after placement. All patients who were randomized will be evaluable for the analysis except patients that require abdominal reoperation within 30 days to address a postoperative complication unrelated to the surgical wound or patients whose BMI is less than 40 who are found to have benign pathology following their surgery. These patients will be considered non-evaluable for primary endpoint. Patients that require any surgical intervention within 30 days specifically to address a wound related complication will be considered evaluable. Patients removed from the study for reasons listed in Section 13 will be included in the analysis as per ITT principle. We will continue accrual until 686 evaluable patients are randomized.

Interim Analysis: The study will be terminated if either the futility or efficacy boundaries are crossed at the interim analysis when 343 evaluable patients have been randomized. The boundaries for the Z-test statistic after half patients (n=343) are enrolled and randomized when the interim analysis will occur are +/-0.246 for futility and +/-2.538 for efficacy. At the end of the study the boundaries will be +/-1.662.

This secondary objective analysis will analyze each type of complication separately namely wound infection, separation, and formation of seroma or hematoma, in a logistic model where the outcome is the presence and absence of wound complication and the covariate of

interest is the intervention arm (A or B). This analysis will be hypothesis generating as we expect very low rates of each one of these outcomes. P-values will not be adjusted for multiplicity.

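### Prevena removal before 2 days is scored as a primary-analysis failure in the NPWT arm only, outside the endpoint definition and with no allowance in the 686-patient calculation

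*Combined protocol and SAP*

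**What the plan says.** Sections 2.0 and 12.0 define the primary endpoint as one or more of wound separation, seroma or hematoma, and infection. Section 12.0 opens its list with "The primary outcome is the observed reduction of wound complications which includes at least one of the following". Sections 4.2 and 9.0 name the same wound events ("An event refers to one of the following") and end follow-up early only when one of them is recorded. Device removal is on none of these lists.

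Section 13.0 puts early Prevena removal under the heading "The following patients will come off study, but they will be included in the analysis" and rules that "the patient will be included in the analysis as a failure". Section 14.0 repeats the rule for the primary analysis ("the patient will be included in the analysis as per ITT and they will be considered as failures") and adds: "We expect that <5% of the enrolled patients will have the Prevena system removed prior to 2 days after placement".

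For the control arm, Section 4.2 says "Patients who randomize to the standard dry gauze arm will have their dressing removed on post-operative day 2 (or before if clinically indicated". No scoring consequence is attached.

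The toxicities section, between Sections 10.0 and 12.0, has the device stopped for severe or lasting side effects. Section 2.0 makes skin reactions a separate tertiary objective: "To report the incidence of adverse events such as blistering and contact dermatitis associated for each arm".

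**The concern.** The two arms are measured with different outcomes. A gauze patient fails only if she has a wound complication. An NPWT patient fails if she has a wound complication or loses the device early.

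Counting an early-removal patient in her assigned arm is ITT. Recording a failure whatever happened to her wound is a separate step, and ITT does not supply it. The result is a one-sided composite that the plan never declares.

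Some reasons for stopping the device, such as rash, pruritus or skin stripping, are not wound complications, so tolerability enters the efficacy endpoint in one arm. Others, such as localized infection or wound deterioration, may overlap with the endpoint.

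The bias runs against NPWT to the extent that removed patients have no true complication. At stake are the power to detect a real halving, the risk of a false finding of harm, and the risk of a futility stop at the interim. The per-arm 30-day complication proportion promised in Section 14.0 would also include NPWT patients who had no complication.

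**Working it through.** **Inputs.** From Section 14.0: control rate 10%, NPWT rate 5%, 80% power, two-sided type I error 10%, total 686, two-sample binomial test, interim at 343 patients (futility ±0.246, efficacy ±2.538), final boundary ±1.662. From Section 15.2: 1:1 allocation. Two quantities are not given and are varied as assumptions: *q*, the early-removal rate in the NPWT arm, and the share of removed patients who also have a true complication.

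**1. The plan's figure.** With pooled variance and mean rate 0.075:

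n per arm = [1.645·√(2·0.075·0.925) + 0.842·√(0.10·0.90 + 0.05·0.95)]² / 0.05² = (0.6127 + 0.3121)² / 0.0025 ≈ 342.1, rounded up to 343, so 686 in total.

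This matches exactly with 5% in the NPWT arm, so no removals were allowed for. Power at 343 per arm is 80.1%.

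**2. Counted NPWT rate under the rule, true halving.**
- Removal independent of outcome: p = q + (1 − q)·0.05
- Half of removed patients have a true complication: p = 0.05 + 0.5q
- All removed patients have one: p = 0.05, and the rule adds nothing

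**3. Power.** With p̄ = (0.10 + p)/2 and n = 343:

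power = Φ{ [(0.10 − p) − 1.645·√(2p̄(1 − p̄)/n)] / √[(0.09 + p(1 − p))/n] }

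Example, q = 1%, independent: p = 0.0595 and p̄ = 0.07975. The numerator is 0.0405 − 0.0340 = 0.0065 and the denominator is 0.0206. The ratio is 0.314, giving power of 62.3%.

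The columns headed *interim* come from simulation with the plan's boundaries (400,000 runs).

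| q | p, indep. | Power, indep. | Interim, indep. | p, half | Power, half | Interim, half |
|---|---|---|---|---|---|---|
| 0 | 5.00% | 80.1% | 79.4% | 5.00% | 80.1% | 79.4% |
| 0.5% | 5.48% | 71.7% | 70.8% | 5.25% | 75.9% | 75.1% |
| 1% | 5.95% | 62.3% | 61.1% | 5.50% | 71.3% | 70.2% |
| 2% | 6.90% | 42.6% | 41.4% | 6.00% | 61.3% | 60.1% |
| 3% | 7.85% | 25.5% | 24.6% | 6.50% | 50.8% | 49.5% |
| 5% | 9.75% | 6.2% | 6.0% | 7.50% | 31.3% | 30.2% |

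Power reaches 70% at q = 0.60% if independent (0.0060 × 343 ≈ 2 patients) and at q = 1.13% with half overlap (0.0113 × 343 ≈ 4 patients).

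**4. No true effect (10% in both arms).** The counted NPWT rate is 0.10 + 0.90q (independent) or 0.10 + 0.5q (half overlap). The chance of a significant result against NPWT, nominally 5%, is 7.6–10.4% at q = 1%, 11.2–18.7% at 2% and 27.1–56.1% at 5%. The lower value is half overlap, the upper independence.

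**5. Interim futility stop under a true halving.** It is 4.8% without the rule, 6.8–8.8% at q = 1%, 9.0–13.3% at 2% and 15.9–21.2% at 5%.

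**6. Denominator.** If the under-5% figure refers to all enrolled patients, it allows up to 0.05 × 686 = 34.3 removals. All would fall in the NPWT arm, so q could approach 34.3/343 = 10%. Under independence, a device that truly halves complications would then show 0.05 + 0.95·0.10 = 14.5% against 10%.

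**The case against.** The rule appears consistently in two sections, so it looks deliberate. Counting intolerance as treatment failure is a recognised composite strategy, and Section 3.0 argues that a costly device should not be adopted unless it proves beneficial. The rule cannot inflate false claims of benefit. Part of the asymmetry is structural, since only Prevena has a required minimum wear time. The reference to ITT can be read as covering inclusion only.

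Early removals may also be few and wound-related. Section 4.1 expects stays of at least 2 days, Section 13.0 has the device removed only for medical reasons when a patient withdraws, and the listed risks include infection and wound deterioration. If three quarters of removed patients had a true complication, the counted rate would be 0.05 + 0.25q and power would be 76% at 1% removal and 71% at 2%.

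Much of this is fair. The bias is conservative for a benefit claim, the 5% rows are an upper figure rather than an expectation, and independence is an assumption. But a deliberate composite still has to be declared in the endpoint and allowed for in the sample size, and neither was done. The rule is harmless only if there are no early removals or every removed patient has a complication; the documents support neither. The secondary models by complication type do not mention the rule, but they are hypothesis-generating and do not repair the primary test.

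**Conclusion.** The concern holds, and the rule must be changed. The primary analysis counts an outcome that the primary objective does not define, in one arm only, and the 80% power stated for 686 patients takes no account of it.

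The loss is material well below the plan's own upper figure. About 2 early removals among 343 bring power to 70% under independence, and about 4 with half overlap. Benefit is harder to show, and false harm and a futility stop become more likely.

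The exact size cannot be fixed, because the removal rate, its denominator and its overlap with true complications are not given. The figures assume the plan's 10% and 5% rates. Independence is not quite the worst case: with no overlap at all, power at 1% removal is 61% rather than 62%. That the rule is one-sided and absent from the endpoint definition needs no assumption.

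**What to change.** In the primary and interim analyses, classify every evaluable randomised patient by her observed 30-day wound outcome in her assigned arm, however long either dressing stayed on. Delete the failure scoring from Sections 13.0 and 14.0. State that early-removal patients remain in the existing day-30 assessment by visit or telephone; as written, their off-study status leaves this unclear. Report early removal separately as an adherence and tolerability outcome, and keep removal-as-failure as a sensitivity analysis. State whether the under-5% figure refers to the NPWT arm or to all enrolled patients.

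The cost is mainly wording, because the day-30 assessment already exists. There are three downsides:
- The primary estimate no longer penalises poor tolerability.
- If accrual has begun, patients already taken off study may lack day-30 data, and the plan then needs a stated rule for them.
- Exactly 80% power is not guaranteed. If removed patients lose all benefit and carry 10% risk, the NPWT rate is 0.05 + 0.05q, and power is about 79% at 1% removal and 76% at 5%.

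The alternative is to declare the composite in the endpoint and re-size the trial. Under independence, that needs 1,106 patients at 1% removal and 1,990 at 2%, which is far more costly.

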Despite the favorable results of these described trials, an equal number of similarly welldesigned studies have demonstrated opposite findings. Randomized controlled trials in the fields of plastic and orthopedic surgery as well as otoloargynology have shown no difference in wound outcomes or rates of incisional drainage, infection, or dehiscence.[28-32] Furthermore, a 2011 randomized trial by Dorafshar et al demonstrated a significantly increased cost to the use of NPWT over standard dressings: \$96 daily for patients in the vac arm as compared to \$4 daily for patients receiving standard gauze dressings.[29] Two more recent cost-benefit analyses, however, illustrated a potential cost savings with the use of NPWT due to the decreases in rates of wound complication and surgical site infection.[33, 34] Echebiri and colleagues posited a prophylactic wound vac cost benefit with SSI rates exceeding 14%.[33] Lewis et al concluded that risk of wound complications must be reduced by 33% for prophylactic NPWT to be a cost effective intervention.[34] To date, there does not exist a consensus on the benefit of NPWT and it is used at the provider's discretion. Given the clear need for optimization of post-operative wound management, as well as the high costs of wound vac therapy, further investigation is warranted.

Currently, there exists a number of options for wound vacuum-assisted closure. Some institutions create their own NPWT device through tubing attachments to standard gauze

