dressing. The PICO system (Smith and Nephew Healthcare, Hull, United Kingdom) is a NPWT that is meant for single, short duration use. The most frequently utilized, and studied, however, is the KCI V.A.C.® negative pressure wound therapy system (KCI, San Antonio, TX). The KCI V.A.C.® is comprised of a closed, sealed system that applies wound suction through the use of an open-celled foam covered with occlusive tape. Intermittent or continuous suction is maintained through tubing that is connected from the foam to a vacuum pump. The standard rate of negative pressure is -125 mmHg. The V.A.C.® therapy platform includes a number of different products for various clinical indications. The Prevena Incision Management System (V.A.C.® Therapy, KCI USA, Inc., San Antonio, TX) is one device intended to manage the environment of clean closed surgical incisions through the removal of wound drainage and exudate via the application of NPWT. The Prevena system is applied immediately post-surgery to the clean closed incision and allowed to remain in place for 2-7 days.

We propose conducting a randomized controlled trial of post-operative wound management with use of the Prevena Incision Management System. We believe the application of a negative pressure wound therapy device placed at completion of surgery may help reduce the rate of surgical site infection and post-operative morbidity. The need for prospective data, particularly in the oncologic community, is significant, and this device can potentially have wide ranging benefits to patients. In addition, the hospital will benefit from the knowledge acquired in this study; given that Prevena Incisions Management System is costly, it should not be adopted for use if it does not prove beneficial to patients.

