14.0 BIOSTATISTICS

An institutional database with information regarding surgical procedures performed by the GYN service at MSK was queried after the institution of a surgical site infection (SSI) reduction bundle in January 2015. Data for the period between 1/1/15 and 6/30/15 demonstrates a total of 248 laparotomies performed for all malignant indications and benign indications for patients with a BMI \geq 40 on the gyn service. 19 cases of wound complication

were noted resulting in a rate of 7.6%. We have chosen a baseline wound complication rate of 10% to take into account potentially higher rates of wound complications in alliance sites that have not yet incorporated an SSI reduction bundle.

Given our known yet unpublished rate of wound-related complications in morbidly obese patients undergoing laparotomy of 27%, it is also important to include this patient population with a clear elevated rate of wound morbidity in our study, even if it will only represent ~1% of our total cases.

With a baseline rate of 10%, we would choose a 50% decrease in the rate of complication to 5% as clinically significant. To achieve 80% power with a type I error of 10% (2 sided test), we will need to enroll a total of 686 patients. Data from our department demonstrates ~38 eligible laparotomies at MSKCC main campus per month. Over the course of the year, this would result in 456 eligible cases per year. If only 30% of eligible patients chose to enroll on study, this would result in 137 patients accruing yearly, which would require 5 years to complete the study.

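### Is a symmetric futility zone of ±0.246 wrong for a trial that asks whether NPWT reduces wound complications?

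*Combined protocol and SAP*

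**What the plan says.** Section 2.0 words the primary objective in one direction: "To determine if prophylactic use of a NPWT system on clean or clean-contaminated, closed incisions reduces incidence of post-operative wound complication". Section 14.0 sizes the trial for a fall from 10% to 5% with 80% power and a "type I error of 10% (2 sided test"), giving 686 patients, and compares the two proportions at that level.

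For the single interim look at 343 evaluable patients, Section 14.0 states: "The study will be terminated if either the futility or efficacy boundaries are crossed at the interim analysis". The Z boundaries there "are +/-0.246 for futility and +/-2.538 for efficacy". For the final analysis: "At the end of the study the boundaries will be +/-1.662".

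The section does not say which sign of Z favours Prevena, and it uses the efficacy label for both signs of 2.538. Section 3.0 says of NPWT that "it is used at the provider's discretion", and of the Prevena system that "it should not be adopted for use if it does not prove beneficial to patients".

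**The concern.** Take positive Z as favouring Prevena. The trial then stops for futility when Z lies between −0.246 and +0.246, and goes on when Z lies between −2.538 and −0.246. A futility rule normally stops a trial whose chance of success has become small. Here every adverse result that continues has a smaller chance of ending in a claim of benefit than any result that stops. If the only question is whether the device reduces complications, the order seems reversed.

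At stake would be up to 343 further women randomised while the device looks worse, in a trial that Section 14.0 expects to need five years of accrual. The plan names no aim of establishing harm that would explain the continuation.

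**Working it through.** **Inputs.** From Section 14.0: rates 10% and 5%, two-sided α = 0.10, power 80%, N = 686, interim at 343 (information fraction 0.5), boundaries ±0.246, ±2.538 and ±1.662. From Section 15.2: 1:1 allocation. Positive Z favours Prevena. Rates of 13% and 15% on Prevena are assumptions, used only to show the effect of harm.

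**1. The plan's sample size.** With pooled variance under the null and no continuity correction, n per arm = [1.645·√(2·0.075·0.925) + 0.842·√(0.10·0.90 + 0.05·0.95)]² / 0.05² = 342.1, rounded up to 343. The total is 686, as stated.

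**2. The plan's boundaries.** Numerical integration of the two-stage Z process, with ±2.538 at the interim, ±1.662 at the end and futility ignored, gives a two-sided type I error of 0.1000. With the futility zone followed it is 0.0961. The zone does not inflate the error.

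**3. The observation behind the concern.** Conditional power for benefit is 1 − Φ((1.662 − r·z)/r − d·r), with r = √0.5 and drift d = 0.05/√((0.09 + 0.0475)/343) = 2.497.

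| Interim Z | Rule | Conditional power for benefit |
|---|---|---|
| +0.246 | edge of stop zone | 36.7% |
| 0 | stop | 27.9% |
| −0.246 | edge of stop zone | 20.3% |
| −0.5 | continue | 13.9% |
| −1 | continue | 5.7% |
| −2 | continue | 0.5% |

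The observation is correct. On the adverse side, however, continuing answers the other half of the two-sided question. Under the current trend, the chance of ending below −1.662 is 36% at Z = −1, 74% at −1.5 and 95% at −2.

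**4. What a one-directional rule would change.** Compare the written rule with stopping at every interim Z below +0.246, the other boundaries unchanged. Expected N = 343 + 343·P(continue).

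*No effect, normal theory.* Written rule: P(continue) = 0.3973 + 0.3973, about 0.7945 before rounding, so expected N = 343 + 343·0.7945 = 615.5. One-directional: 343 + 343·0.3973 = 479.3.

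*Design effect, normal theory.* Written rule: P(continue) = 0.7157 + 0.0221 = 0.7378, so expected N = 596.1. One-directional: 343 + 343·0.7157 = 588.5. Only 2.2% of trials continue on the adverse side.

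Binomial simulation (4,000,000 trials per scenario, 172 and 171 patients at the interim, 343 per arm at the end, pooled Z) gives:

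| True rates, gauze vs Prevena | Quantity | Written rule | One-directional |
|---|---|---|---|
| 10% vs 10% | Expected N | 609 | 478 |
| 10% vs 10% | False claim of benefit | 0.0484 | 0.0480 |
| 10% vs 10% | False claim of harm | 0.0483 | 0.0062 |
| 10% vs 5% | Power for benefit | 79.4% | 79.2% |
| 10% vs 5% | Expected N | 599 | 592 |
| 10% vs 13% (assumed) | Chance of showing harm | 33% | 5% |
| 10% vs 13% (assumed) | Expected N | 622 | 389 |
| 10% vs 15% (assumed) | Chance of showing harm | 62% | 13% |
| 10% vs 15% (assumed) | Expected N | 617 | 361 |

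**5. What remains of the declared test.** Under the one-directional rule the total type I error is 0.0480 + 0.0062 = 0.054, against about 0.096 under the written rule (normal theory 0.0961). The lower side keeps almost only the −2.538 interim boundary. That is close to a one-sided 5% test with a small harm stop, not the two-sided 10% test of Section 14.0.

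**The case for a change.** The strongest case for the concern is that a two-sided α does not oblige anyone to use two-sided futility. The objective and the adoption statement in Section 3.0 both concern benefit, and the safety objective is descriptive. With no true effect, about 38% of trials continue with Prevena looking worse, and only 0.1% of those end in a claim of benefit. Section 16.2 describes a DSMB for phase III trials but gives no rule for this region. In addition, removal of Prevena before 2 days counts as a failure, with no matching rule for gauze. If 2% of Prevena patients were affected (an assumption, within the under-5% the plan expects), no true effect would appear as 0.02 + 0.98·10% = 11.8% vs 10%, and adverse trends would be more frequent.

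The figures stand, and so does the saving: a designer interested only in benefit could reasonably choose one-directional futility. That does not make the written rule wrong. By declaring a two-sided test the plan has already taken an interest in both directions, and the documents give reasons to value it. Section 3.0 reports trials that favour NPWT and as many that do not, for a therapy already in discretionary use. The device risk table after Section 10.0 lists localized infection and wound deterioration because the incision cannot be seen. Separating no benefit from harm is useful in that setting. The early-removal point concerns how failures are scored; it would tilt the primary comparison under either futility rule.

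The undefined sign of Z and the efficacy label on the lower boundary are gaps in wording. The boundaries are symmetric, so every stopping decision is the same whichever sign is used.

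**Conclusion.** The concern does not hold. A symmetric inner futility zone suits the two-sided 10% test that Section 14.0 declares, keeps type I error at or below 0.100, and reproduces with the plan's other figures. It does allow continuation where benefit has become unlikely, but in those cases the trial is still testing for a difference in the other direction. A one-directional rule would trade a saving of about 130 patients with no effect (609 − 478 = 131), and larger savings under harm, for most of the ability to show harm (33% to 5%, and 62% to 13%, at assumed rates of 13% and 15%). That is a design preference. Labelling the lower boundaries as harm and stating why the trial continues on that side would make the text clearer, but would change no decision under the written rule.

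The figures rest on an interim at exactly half the information, a pooled Z test, a 10% gauze rate and boundaries applied as written.
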